6.3. Radiation Therapy

Refer to **Appendix 3 for UAB Department of Radiation Oncology Treatment Practice Guidelines** for further details of radiation therapy.

Brachytherapy boost will not be permitted.

6.3.1 Target Volume

Dose inhomogeneity ranges for PTV coverage will be 95% of PTV volume will receive 100% of prescribed dose; 100% of PTV volume will receive 95% of dose. Global hotspot <107%.

Minor deviation that is acceptable: 90% of PTV receiving 100% of dose; 95% PTV receive 95% of dose; global hotspot 110%.

6.3.2 Compliance

Treatment plans will be peer-reviewed for compliance prior to starting radiation at the weekly treatment planning conference.

6.4. Dose modifications of Study drugs

6.4.1. Planned Dose modifications

Intrasubject dose escalations are not permitted. **Table 4** describes Abemaciclib dose reductions that may occur due to any related AEs. There will be no dose reductions of LHRH analogues allowed for the management of toxicities of individual subjects. Doses of ADT may be delayed for toxicity management.

Table 4: Allowable Abemaciclib Dose Modifications for Toxicity Attributed to Abemaciclib

Cohort	Current Dose	Dose Reduction
1	150 mg BID	100 mg BID

6.4.2. Criteria and Procedure for interruption

In some circumstances, it may be necessary to temporarily interrupt study treatments as a result of AEs that may have an unclear relationship to the study drug(s). If an interruption is necessary, both study treatments should be interrupted.

Any dose interruptions of > 2 weeks for LFT abnormalities must be discussed with the medical monitor before resuming treatment. Treatment with both study drugs should be withheld for drug-related Grade 4 hematologic toxicities, non-hematological toxicity \geq Grade 3 (including laboratory abnormalities), and severe or life-threatening AEs.

Except in cases of emergency, it is recommended that the investigator consult with the sponsor's medical monitor (or other representative of the sponsor) before temporarily interrupting therapy for reasons other than Protocol-mandated medication hold. Additionally, the investigator must notify the sponsor's medical monitor and study project manager via email or during safety teleconferences before restarting study drug that was temporarily interrupted because of an AE.

Dose modifications for hematologic and non-hematologic AEs related to chemotherapy may be managed per institutional guidelines.

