All patients will receive 150 mg Abemaciclib PO BID for 28 days. Patients will receive treatment with Abemaciclib until there is (are) toxicity(ies) or disease progression on treatment or withdrawal from study for any reason. All patients will receive ADT using LHRH analogues every 3 months along with Abemaciclib. There will be no intra patient dose escalation in dosing of Abemaciclib. Patients will take Abemaciclib in clinic on Day 1 of each cycle. They can take the rest of the pills at home. Radiation Therapy will be scheduled at 3 months after C1D1 (Abemaciclib and ADT). Abemaciclib will be stopped 2 weeks before Radiation Therapy and resumed with first dose of ADT after Radiation therapy is completed (usually 1 month after completion of RT). Abemaciclib will continue along with ADT for 24 months (+/- 3 days).

ADT Dose and Administration:

ADT using LHRH analogues will be administered SC beginning on C1D1 and continue during radiation and after radiation for a total of 24 months (+/-3 days) in the absence of toxicity. Dose modification of the ADT is not allowed.

Duration of Treatment:

Patients are eligible for abemaciclib treatment until unacceptable toxicity, or withdrawal of consent, or progression of disease on treatment or maximum of 24 months of ADT on the study. A patient should be withdrawn from study treatment if, in the opinion of the Investigator, it is medically necessary, or if it is the wish of the patient. In addition, patients will be withdrawn from treatment in the case of:

1. A need for surgery, radiation, or for other anticancer therapy not permitted by this protocol
2. Lost to follow-up or noncompliant with the protocol
3. Any Abemaciclib dose delay > 7 days during the first cycle

Parameters to be Assessed:Safety:

Safety assessments will include physical examinations, vital signs, ECOG performance status, laboratory tests (complete blood counts [CBC] and serum chemistry), 12-lead electrocardiograms (ECGs), and additional studies as may be clinically indicated.

Exploratory Biomarkers:

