Interstitial lung disease (ILD) /pneumonitis has been identified as an adverse drug reaction for abemaciclib. The majority of events observed in clinical trials were Grade 1 or Grade 2 with serious cases and fatal events reported. Additional information is available in the IB.

Monitor for clinical symptoms or radiological changes indicative of ILD/pneumonitis and ask your patients to report any new or worsening pulmonary symptoms such as dyspnea, cough, and fever, and investigate and treat as per your local clinical practice (including corticosteroids as appropriate). If ILD/pneumonitis is suspected, investigations may include imaging, such as high resolution computed tomography, bronchoalveolar lavage, and biopsy as clinically indicated. Discontinue abemaciclib in cases of severe (Grade 3 or 4) ILD/pneumonitis.

Table 6: Dose Modification and Management — Interstitial Lung Disease/Pneumonitis

CTCAE Grade	Abemaciclib Dose Modifications
Grade 1 or 2	No dose modification is required.
Persistent or recurrent Grade 2 toxicity that does not resolve with maximal supportive measures within 7 days to baseline or Grade 1	Suspend dose until toxicity resolves to baseline or Grade 1. Resume at next lower dose.
Grade 3 or 4	Discontinue abemaciclib.

General Guidance for Hepatic Monitoring

Alanine aminotransferase (ALT) and aspartate aminotransferase (AST) elevation are considered as ADR with the use of abemaciclib. **The following information in Table 7 on hepatic monitoring:**

Table 7: Dose Modification and Management — Increased ALT/AST

Monitor ALT/AST prior to the start of abemaciclib therapy, every 2 weeks for the first 2 months, monthly for the next 2 months, and as clinically indicated.	
CTCAE Grade	Abemaciclib Dose Modifications
Grade 1 ($>\text{ULN}-3.0 \times \text{ULN}$) Grade 2 ($>3.0-5.0 \times \text{ULN}$)	No dose modification is required.
Persistent or Recurrent Grade 2, or Grade 3 ($>5.0-20.0 \times \text{ULN}$) that does not resolve with maximal supportive measures within 7 days to baseline or Grade 1: suspend dose until toxicity resolves to baseline or Grade 1.	Suspend dose until toxicity resolves to baseline or Grade 1. Resume at next lower dose.
$\geq\text{Grade 2} (>3.0 \times \text{ULN})$ with total bilirubin $>2 \times \text{ULN}$, in the absence of cholestasis	Discontinue abemaciclib
Grade 4 ($>20.0 \times \text{ULN}$)	Discontinue abemaciclib.

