Hematologic toxicities including neutropenia, leukopenia, anemia, and thrombocytopenia have been observed in patients treated with abemaciclib, and causality has been established. Severe (Grade 3 and 4) neutropenia was observed in patients receiving abemaciclib. Patients should be monitored closely for signs of infection, anemia, and bleeding. **Table 9 provides guidance on dose modification and management of hematologic toxicities.**

Table 9: Dose Modification and Management — Hematologic Toxicities

Monitor complete blood counts prior to the start of abemaciclib therapy, every 2 weeks for the first 2 months, monthly for the next 2 months, and as clinically indicated.	
CTCAE Grade	Abemaciclib Dose Modifications
Grade 1 or 2	No dose modification is required.
Grade 3	Suspend dose until toxicity resolves to \leq Grade 2. Dose reduction is not required.
Grade 3, recurrent, or Grade 4	Suspend dose until toxicity resolves to \leq Grade 2. Resume at next lower dose.
Patient requires administration of a blood cell growth factor	Suspend abemaciclib dose for at least 48 hours after the last dose of blood cell growth factor and until toxicity resolves to \leq Grade 2. Resume abemaciclib at next lower dose unless the dose was already reduced for the toxicity that led to the use of the growth factor.

General Guidance for Non-hematologic Toxicities (excluding diarrhea, ILD/Pneumonitis and increased ALT/AST) Monitoring

Table 10: Dose Modification and Management — Non-hematologic Toxicities Excluding Diarrhea and ALT Increased

CTCAE Grade	Abemaciclib Dose Modifications
Grade 1 or 2	No dose modification is required.
Persistent or recurrent Grade 2 toxicity that does not resolve with maximal supportive measures within 7 days to baseline or Grade 1	Suspend dose until toxicity resolves to baseline or Grade 1. Resume at next lower dose.
Grade 3 or 4	

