8.3.6. Relationship to Treatment Drugs (Abemaciclib)

In this study, there are 2 study drugs; the investigational drug Abemaciclib is given in combination with ADT. The relationship of each AE to each study drug will be made and

should be guided in part by the known safety profile of each drug, including the Abemaciclib IB. The relatedness should be classified by the Investigator using the following guidelines:

- Suspected Adverse Reaction: There is a reasonable possibility that study drug caused the AE (i.e., there is evidence to suggest a causal relationship between study drug and the AE).
- Not Related: There is no reasonable possibility that the AE is associated with study drug.

AEs related to study drug are considered Adverse Drug Reactions (ADR).

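### Section 6.4.2, the dose-modification tables and Table 1 give different instructions for the same toxicity, and whether ADT is held is not stated consistently

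*Combined protocol and SAP*

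**What the plan says.** **Which drugs are meant.** Section 8.3.6: "In this study, there are 2 study drugs; the investigational drug Abemaciclib is given in combination with ADT".

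**Section 6.4.2.** For adverse events whose link to study drug is unclear: "If an interruption is necessary, both study treatments should be interrupted". For graded toxicity: "Treatment with both study drugs should be withheld for drug-related Grade 4 hematologic toxicities". The same sentence adds non-hematologic toxicity of Grade 3 or more, including laboratory abnormalities, and severe or life-threatening events. It sets no waiting period.

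**Section 6.4.3.** Tables 5, 6, 7, 9 and 10 each have one action column, for abemaciclib. The usual instruction begins "Suspend dose until toxicity resolves to", followed by a grade that depends on the toxicity. Some rows discontinue abemaciclib instead.

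**Table 1 (section 4.1.1) and the matching synopsis table.** Patients are withdrawn for drug-related Grade 3 or 4 non-hematologic toxicity, with two short-lived exceptions, and for several hematologic events.

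**ADT.** The synopsis says "Dose modification of the ADT is not allowed", and that ADT runs "for a total of 24 months (+/-3 days) in the absence of toxicity". Section 6.4.1 bars dose reductions of LHRH analogues but adds "Doses of ADT may be delayed for toxicity management".

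**Time limits.** Section 5.3 and the synopsis withdraw a patient from treatment for an abemaciclib delay of more than 7 days in cycle 1. Section 6.5 does so for toxicity that has not recovered in 2 weeks, unless the medical monitor approves continuing.

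**The concern.** An investigator facing a foreseeable event has several current instructions and no rule of precedence. They differ on which drug is stopped, when, and whether treatment can resume. Two patients with the same laboratory result could be managed differently while each investigator follows the protocol.

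There is also a possible analysis consequence. The primary endpoint is a PSA nadir during treatment, and time to PSA failure is secondary. ADT acts on testosterone and PSA, so an injection delayed because of an abemaciclib side effect could move PSA for a reason unrelated to abemaciclib's activity. It would do so only in patients with toxicity. The statistics section does not say how PSA measured during a hold counts.

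**Working it through.** **1. The instructions side by side.** The action for Grade 3 or 4 in Table 5 is read as the cell it appears to share with the row above; this is an assumption about the layout.

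| Event | Section 6.4.2 | Section 6.4.3 table | Table 1 (if drug-related) |
|---|---|---|---|
| Grade 3 ALT/AST | withhold both drugs, no wait | Table 7: suspend abemaciclib if unresolved within 7 days, resume lower | withdraw |
| Grade 4 ALT/AST | withhold both | Table 7: discontinue abemaciclib | withdraw |
| Grade 3 or 4 ILD/pneumonitis | withhold both | Table 6: discontinue abemaciclib | withdraw |
| Grade 3 or 4 diarrhea | withhold both | Table 5: suspend abemaciclib, resume lower | withdraw |
| Grade 3 hematologic, first occurrence | not in the grade list, which starts at Grade 4 | Table 9: suspend abemaciclib, same dose on resuming | not listed alone |
| Grade 4 anemia or thrombocytopenia | withhold both | Table 9: suspend abemaciclib, resume lower | withdraw |

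In five of the six rows the three sources do not agree. In the Grade 3 hematologic row, section 6.4.2 is itself unclear. Its grade list names Grade 4, but it also covers severe events, and section 6.4.3 uses that word for Grade 3 and 4 neutropenia.

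**2. Size of the timing gap for Grade 3 ALT/AST.** Section 6.4.2 starts the hold at day 0; Table 7 as worded starts it after up to 7 days. At two doses a day the difference is 7 × 2 = 14 doses.

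**3. Interaction with the cycle 1 limit.** Let the event last d days within cycle 1, and assume each hold ends at resolution (section 6.4.2 does not say when its hold ends).

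- Section 6.4.2: abemaciclib is off for d days, over the limit when d > 7.
- Table 7: abemaciclib is off for d − 7 days, over the limit when d − 7 > 7, that is d > 14.

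For 7 < d ≤ 14, the same event ends treatment under section 6.4.2 and not under Table 7. If Table 1 is followed, the patient is withdrawn in either case.

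**4. Can an ADT hold reach the PSA endpoints?** ADT is given on C1D1 and then every 3 months, about every 13 weeks. Over 24 months that is 24 / 3 = 8 injections.

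- PSA at 6 weeks, the time in the alternative hypothesis in section 10.1: 6 < 13, so no second injection is due and an ADT hold cannot act.
- Nadir during treatment (section 10.2.1): an effect is possible only if an injection falls due during a hold. A nadir is a minimum, so a later hold cannot undo one already reached.
- Time to PSA failure: an effect is possible on the same condition.

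**5. The design's own figures.** The two-stage rule (stop on 0 of 5; reject the null on 4 or more of 23) reproduces. The exact type I error is 0.0174 at 5%, within the stated 0.025, and power is 0.806 at 30%. This point does not change them.

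For illustration only, suppose a share f of patients is held and their response probability is multiplied by m, so p = 0.30 × (1 − f + f × m). Neither f nor m is in the documents.

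| f | m | p | Power |
|---|---|---|---|
| any | 1 | 0.300 | 80.6% |
| 5% | 0.5 | 0.2925 | 79.2% |
| 10% | 0.5 | 0.285 | 77.8% |
| 20% | 0.5 | 0.270 | 74.7% |
| 20% | 0 | 0.240 | 67.1% |

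The result depends entirely on f and m, so it is not an estimate for this trial.

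**The case against.** **The tables are silent on ADT, and silence is not contradiction.** This is fair as far as it goes: Table 5 does not say that a due injection is given. Section 6.4.2 and Table 9 can also be read as tiers, with abemaciclib suspended at Grade 3 and both drugs withheld at Grade 4. That does not rescue the other rows. Withholding, discontinuing and withdrawing are different actions, and Table 7's 7-day condition has no counterpart in section 6.4.2.

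**Table 7's 7-day clause might attach only to Grade 2.** The row allows that reading with some strain. The timing gap would then go, but the differences in drug and outcome would remain.

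**The general interruption sentence concerns events of unclear relationship, while section 6.4.3 concerns abemaciclib-related events.** This stands. The firm conflict rests on the later sentence about both study drugs.

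**A reader might infer that the synopsis flatly forbids interrupting ADT.** The documents do not support that. Dose modification can mean the amount given, in line with section 6.4.1, and the synopsis itself conditions ADT duration on absence of toxicity. What remains is an unclear rule: no modification in one place, delay permitted in another, withholding directed in a third.

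**A reader might infer that the conflict produces a different PSA outcome.** This is not shown. The 6-week reading is out of reach of an ADT hold, and the pre-radiotherapy decline is essentially covered by the first injection. The progression rule needs three consecutive rises 3 months apart with testosterone recovery, and nothing in the documents says a short delay would bring that recovery about.

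**A reader might size the problem from the toxicity rates in section 2.3.2.** Those are breast cancer figures for Grade 3 or higher neutropenia and any-grade diarrhea. They do not match the section 6.4.2 triggers, which start at Grade 4 for hematologic toxicity and Grade 3 for diarrhea.

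**Conclusion.** The concern holds as an internal inconsistency with patient-safety consequences. One event can lead to a hold of both drugs, a hold of abemaciclib alone, a hold that starts later, discontinuation of abemaciclib, or withdrawal of the patient. The plan does not say which instruction prevails. The measurable part is a gap of up to 7 days, or 14 abemaciclib doses, for Grade 3 ALT/AST. In cycle 1 that gap can decide whether the 7-day delay limit is crossed. Both results assume that Table 7's 7-day clause applies to Grade 3; the cycle 1 result also assumes that holds end at resolution.

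The effect on endpoints is secondary. It is possible for the on-treatment nadir and for time to PSA failure when an injection falls due during a hold. It is excluded, through ADT, for a 6-week PSA. Its size cannot be derived from the documents and may be nil. The case for amending rests on the contradictory instructions and does not need the PSA argument.

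**What to change.** Reconcile the synopsis toxicity table and ADT paragraph, Table 1, sections 6.4.1, 6.4.2 and 6.5, and Tables 5, 6, 7, 9 and 10. Each toxicity should then have one action, one grade and time trigger, and the drug or drugs named. Check the result against the cycle 1 delay limit in section 5.3. Add one sentence saying which section governs if two still overlap, and state what happens when an ADT injection falls due during a hold. Table 1 and section 6.5 must be included, or a further outcome for the same events will remain. Which clinical rule to adopt is for the sponsor.

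Optionally, list patients whose ADT injection was delayed for toxicity, with their primary and time-to-PSA-failure results, using dates and testosterone values already collected.

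Cost: a protocol wording amendment and, if wanted, one extra listing. No added patients or visits, and no change to the sample size or decision rule.

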6.4.3. Procedures for management of Abemaciclib related adverse event(s)

Guidelines for Diarrhea Management

Clinical trial data indicates the majority of patients who receive abemaciclib will develop diarrhea. Our experience indicates early identification and intervention for the management of diarrhea has been helpful to patients.

At enrollment, patients should receive instructions on the prompt management of diarrhea. In the event of diarrhea, supportive care measures should be initiated as early as possible. These include the following:

- At the first sign of loose stools, the patient should initiate antidiarrheal therapy (e.g. loperamide) and notify the investigator for further instructions and appropriate follow-up.
- Patients should also be encouraged to drink fluids (e.g., 8 to 10 glasses of clear liquids per day).
- Site personnel should assess response within 24 hours.
- Refer to Table 5 for additional information for diarrhea management and dose modification.

Table 5: Dose Modification and Management- Diarrhea

At the first sign of loose stools, start treatment with antidiarrheal agents, such as loperamide.	
CTCAE Grade	Abemaciclib Dose Modifications
Grade 1	No dose modification is required.
Grade 2	If toxicity does not resolve within 24 hours to \leq Grade 1, suspend dose until resolution. Dose reduction is not required.
Grade 2 that persists or recurs after resuming the same dose despite maximal supportive measures	Suspend dose until toxicity resolves to \leq Grade 1. Resume at next lower dose.
Grade 3 or 4 or requires hospitalization	

General Guidance for Increases in Serum Creatinine and Assessment of Renal Insufficiency

Elevation of serum creatinine is observed with abemaciclib, and is due to a pharmacological inhibitory effect of abemaciclib on renal tubular transporters without affecting glomerular function. The rise in serum creatinine (mean increase, 0.2 mg/dL) occurs within the first 28-day cycle of abemaciclib, and remains elevated but stable throughout the treatment period, and were reversible upon treatment discontinuation. Alternative markers (such as BUN, cystatin C level, or cystatin C calculated GFR) which are not based on creatinine, may be considered to determine whether renal function is impaired.

General Guidance for Interstitial lung disease (ILD)/Pneumonitis events

Interstitial lung disease (ILD) /pneumonitis has been identified as an adverse drug reaction for abemaciclib. The majority of events observed in clinical trials were Grade 1 or Grade 2 with serious cases and fatal events reported. Additional information is available in the IB.

Monitor for clinical symptoms or radiological changes indicative of ILD/pneumonitis and ask your patients to report any new or worsening pulmonary symptoms such as dyspnea, cough, and fever, and investigate and treat as per your local clinical practice (including corticosteroids as appropriate). If ILD/pneumonitis is suspected, investigations may include imaging, such as high resolution computed tomography, bronchoalveolar lavage, and biopsy as clinically indicated. Discontinue abemaciclib in cases of severe (Grade 3 or 4) ILD/pneumonitis.

Table 6: Dose Modification and Management — Interstitial Lung Disease/Pneumonitis

CTCAE Grade	Abemaciclib Dose Modifications
Grade 1 or 2	No dose modification is required.
Persistent or recurrent Grade 2 toxicity that does not resolve with maximal supportive measures within 7 days to baseline or Grade 1	Suspend dose until toxicity resolves to baseline or Grade 1. Resume at next lower dose.
Grade 3 or 4	Discontinue abemaciclib.

General Guidance for Hepatic Monitoring

Alanine aminotransferase (ALT) and aspartate aminotransferase (AST) elevation are considered as ADR with the use of abemaciclib. **The following information in Table 7 on hepatic monitoring:**

Table 7: Dose Modification and Management — Increased ALT/AST

Monitor ALT/AST prior to the start of abemaciclib therapy, every 2 weeks for the first 2 months, monthly for the next 2 months, and as clinically indicated.	
CTCAE Grade	Abemaciclib Dose Modifications
Grade 1 ($>\text{ULN}-3.0 \times \text{ULN}$) Grade 2 ($>3.0-5.0 \times \text{ULN}$)	No dose modification is required.
Persistent or Recurrent Grade 2, or Grade 3 ($>5.0-20.0 \times \text{ULN}$) that does not resolve with maximal supportive measures within 7 days to baseline or Grade 1: suspend dose until toxicity resolves to baseline or Grade 1.	Suspend dose until toxicity resolves to baseline or Grade 1. Resume at next lower dose.
$\geq\text{Grade 2} (>3.0 \times \text{ULN})$ with total bilirubin $>2 \times \text{ULN}$, in the absence of cholestasis	Discontinue abemaciclib
Grade 4 ($>20.0 \times \text{ULN}$)	Discontinue abemaciclib.

Details for hepatic monitoring depend upon the severity and persistence of observed laboratory test abnormalities are shown below in Table 7.

Table 8: Hepatic Monitoring Tests for a Hepatic Treatment Emergent Abnormality.

Hematology	Clinical Chemistry
Hemoglobin	Total bilirubin
Hematocrit	Direct bilirubin
Erythrocytes (RBCs - red blood cells)	Alkaline phosphatase (ALP)
Leukocytes (WBCs - white blood cells)	Alanine aminotransferase (ALT)
Differential:	Aspartate aminotransferase (AST)
Neutrophils, segmented	Gamma-glutamyl transferase (GGT)
Lymphocytes	Creatine kinase (CK)
Monocytes	Other Chemistry
Basophils	Acetaminophen
Eosinophils	Acetaminophen protein adducts
Platelets	Alkaline phosphatase isoenzymes
Cell morphology (RBC and WBC)	Ceruloplasmin
	Copper
Coagulation	Ethyl alcohol (EtOH)
Prothrombin time, INR (PT-INR)	Haptoglobin
Serology	Immunoglobulin IgA (quantitative)
Hepatitis A virus (HAV) testing:	Immunoglobulin IgG (quantitative)
HAV total antibody	Immunoglobulin IgM (quantitative)
HAV IgM antibody	Phosphatidylethanol (PEth)
Hepatitis B virus (HBV) testing:	Urine Chemistry
Hepatitis B surface antigen (HBsAg)	Drug screen
Hepatitis B surface antibody (anti-HBs)	Ethyl glucuronide (EtG)
Hepatitis B core total antibody (anti-HBc)	Other Serology
Hepatitis B core IgM antibody	Anti-nuclear antibody (ANA)
Hepatitis B core IgG antibody	Anti-smooth muscle antibody (ASMA) a
HBV DNA c	Anti-actin antibody b
Hepatitis C virus (HCV) testing:	Epstein-Barr virus (EBV) testing:
HCV antibody	EBV antibody
HCV RNA c	EBV DNA c
Hepatitis D virus (HDV) testing:	Cytomegalovirus (CMV) testing:
HDV antibody	CMV antibody
Hepatitis E virus (HEV) testing:	CMV DNA c

HEV IgG antibody	Herpes simplex virus (HSV) testing:
HEV IgM antibody	HSV (Type 1 and 2) antibody
HEV RNA c	HSV (Type 1 and 2) DNA c
Microbiology	Liver kidney microsomal type 1 (LKM-1) antibody
Culture:	
Blood	
Urine	

- a Not required if anti-actin antibody is tested.
- b Not required if anti-smooth muscle antibody (ASMA) is tested.
- c Reflex/confirmation dependent on regulatory requirements, testing availability, or both.

General Guidance for Hematology Toxicity and Dose Modification

Hematologic toxicities including neutropenia, leukopenia, anemia, and thrombocytopenia have been observed in patients treated with abemaciclib, and causality has been established. Severe (Grade 3 and 4) neutropenia was observed in patients receiving abemaciclib. Patients should be monitored closely for signs of infection, anemia, and bleeding. **Table 9 provides guidance on dose modification and management of hematologic toxicities.**

Table 9: Dose Modification and Management — Hematologic Toxicities

Monitor complete blood counts prior to the start of abemaciclib therapy, every 2 weeks for the first 2 months, monthly for the next 2 months, and as clinically indicated.	
CTCAE Grade	Abemaciclib Dose Modifications
Grade 1 or 2	No dose modification is required.
Grade 3	Suspend dose until toxicity resolves to \leq Grade 2. Dose reduction is not required.
Grade 3, recurrent, or Grade 4	Suspend dose until toxicity resolves to \leq Grade 2. Resume at next lower dose.
Patient requires administration of a blood cell growth factor	Suspend abemaciclib dose for at least 48 hours after the last dose of blood cell growth factor and until toxicity resolves to \leq Grade 2. Resume abemaciclib at next lower dose unless the dose was already reduced for the toxicity that led to the use of the growth factor.

General Guidance for Non-hematologic Toxicities (excluding diarrhea, ILD/Pneumonitis and increased ALT/AST) Monitoring

Table 10: Dose Modification and Management — Non-hematologic Toxicities Excluding Diarrhea and ALT Increased

CTCAE Grade	Abemaciclib Dose Modifications
Grade 1 or 2	No dose modification is required.
Persistent or recurrent Grade 2 toxicity that does not resolve with maximal supportive measures within 7 days to baseline or Grade 1	Suspend dose until toxicity resolves to baseline or Grade 1. Resume at next lower dose.
Grade 3 or 4	

